14.5 Confidentiality

Patient medical information obtained by this study is confidential and may be disclosed to third parties only as permitted by the ICF (or separate authorization to use and disclose personal health information) signed by the patient or unless permitted or required by law.

Medical information may be given to a patient's personal physician or other appropriate medical personnel responsible for the patient's welfare for treatment purposes.

Data generated by this study must be available for inspection upon request by representatives of the FDA and other regulatory agencies, national and local health authorities, Genentech representatives and collaborators, and the IRB/Ethics Committee (EC) for each study site, if appropriate.

Information about study subjects will be kept confidential and managed according to the requirements of the Health Insurance Portability and Accountability Act (HIPAA). Those regulations require a signed subject authorization informing the subject of the following:

- What protected health information (PHI) will be collected from subjects in this study
- Who will have access to that information and why
- Who will use or disclose that information
- The rights of a research subject to revoke their authorization for use of their PHI.

In the event that a subject revokes authorization to collect or use PHI, the investigator, by regulation, retains the ability to use all information collected prior to the revocation of subject authorization. For subjects that have revoked authorization to collect or use PHI, attempts should be made to obtain permission to collect at least vital status (e.g., that the subject is alive) at the end of their scheduled study period.

The subject binders will be maintained with in the CPDM offices, a secured floor within the Herbert Irving Pavilion and only the investigator and study staff will have access to the file.

14.6 Source Documents

Source data is all information, original records of clinical findings, observations, or other activities in a clinical trial necessary for the reconstruction and evaluation of the trial. Source data are contained in source documents. Examples of these original documents, and data records include: hospital records, clinical and office charts, laboratory notes, memoranda, subjects' diaries or evaluation checklists, pharmacy dispensing records, recorded data from automated instruments, copies or transcriptions certified after verification as being accurate and complete, microfiches,

photographic negatives, microfilm or magnetic media, x-rays, subject files, and records kept at the pharmacy, at the laboratories, and at medico-technical departments involved in the clinical trial.

14.7 Case Report Forms

The study case report form (CRF) is the primary data collection instrument for the study. All data requested on the CRF must be recorded. All missing data must be explained. If a space on the CRF is left blank because the procedure was not done or the question was not asked, write “N/D”. If the item is not applicable to the individual case, write “N/A”.

14.8 Records Retention

FDA regulations (21 CFR §312.62[c]) and the ICH Guideline for GCP (see Section 4.9 of the guideline) require that records and documents pertaining to the conduct of clinical trials and the distribution of investigational drug, patient records, consent forms, laboratory test results, and medication inventory records, must be retained for 2 years after the last marketing application approval in an ICH region or after at least 2 years have elapsed since formal discontinuation of clinical development of the investigational product. All state and local laws for retention of records also apply.

This minimum retention period applies whether or not any subjects were enrolled in the study.

Clinical records, including consent forms that document clinical intervention or clinical diagnostic procedure research-related procedures, must be retained in medical records by the institution for at least seven years, per CUIMC and NYP policy which is based on state law.

15 STATISTICAL CONSIDERATIONS

15.1 Study Design

This is a single-arm, open-label phase II study to assess the efficacy of liver-directed SBRT added to first-line atezolizumab, carboplatin, and etoposide in ES-SCLC patients as measured by 6-month PFS (primary endpoint). We hypothesize that the addition of SBRT will increase the 6-month PFS from 20% (historical control rate) to 45%. A single-stage design based on one-sided exact binomial test will be used, with a type I error of 0.10 and a power of 80%. This design requires a total of 16 evaluable patients. If at least 6 out of 16 patients have not experienced progression at 6 months, this combination therapy will be considered worthy of further study. In order to account for an estimated 10% dropout rate, 18 patients will be accrued to this study.

Primary endpoint:

- 6-month PFS rate will be defined as the proportion of patients that are progression free and alive at 6 months from the start of treatment.

Secondary endpoints:

- Overall survival (OS) will be defined as the time from treatment start to date of death or last follow up. Patients lost to follow-up at the cut-off date will be censored in the analysis.

- Overall response rate (ORR) will be defined as the proportion of patients who have a partial (PR) or complete response (CR) after beginning study treatment. Only patients who have received at least one cycle of therapy and have had their disease re-evaluated will be considered evaluable for response (see [Section 13.5.2](#)).
- Disease control rate (DCR) will be defined as the proportion of patients who have a partial (PR) or complete response (CR) or stable disease (SD) after beginning study treatment. Only patients who have received at least one cycle of therapy and have had their disease re-evaluated will be considered evaluable for response (see [Section 13.5.3](#)).
- Best overall response (BOR) will be defined as the best response recorded from the start of the treatment until disease progression (see [Section 13.5.4](#)).
- Duration of response will be defined as measured from the time measurement criteria are met for CR or PR until the first date that recurrent or progressive disease is objectively documented (see [Section 13.6](#))
- The safety and tolerability of liver-directed SBRT will be determined by reported AEs, physical examinations and laboratory tests. Frequencies of toxicities by grade according to NCI CTCAE (version 5.0) will be tabulated.
- In-field local control will be defined as the absence of disease progression within the planning target volume (PTV) as per RECIST v1.1 on CT at 6 months following radiation treatment
- Out of field disease progression will be defined as the development of lesions outside the PTV as assessed by RECIST v1.1 criteria at 6 months following radiation treatment

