13 MEASUREMENT OF EFFECT

13.1 Antitumor Effect – Solid Tumors

For the purposes of this study, patients will undergo a baseline scan during screening and should be re-evaluated for response every 6 weeks for 12 months beginning within -7d of Cycle 4, Day 1 and thereafter every 9 weeks.

Response and progression will be evaluated in this study using the international criteria proposed by the revised Response Evaluation Criteria in Solid Tumors (RECIST) guideline (version 1.1)⁵³. Changes in the largest diameter (unidimensional measurement) of the tumor lesions and the shortest diameter in the case of malignant lymph nodes are used in the RECIST criteria.

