13.2 Definitions

Evaluable for toxicity: All patients will be evaluable for toxicity from the time of their first treatment with atezolizumab, carboplatin and etoposide.

Evaluable for objective response: Only those patients who have measurable disease present at baseline, have received at least one cycle of therapy, and have had their disease re-evaluated will be considered evaluable for response. These patients will have their response classified according to the definitions stated below. (Note: Patients who exhibit objective disease progression prior to the end of cycle 1 will also be considered evaluable.)

Evaluable Non-Target Disease Response: Patients who have lesions present at baseline that are evaluable but do not meet the definitions of measurable disease, have received at least one cycle of therapy, and have had their disease re-evaluated will be considered evaluable for non-target disease. The response assessment is based on the presence, absence, or unequivocal progression of the lesions. SBRT-treated liver lesions should not be counted as target lesions for disease response.

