15.2 Analytical Plan

Descriptive statistics will be used to describe all the study endpoints. Mean (standard deviation) and/or median (interquartile range) will be used to summarize the continuous variables. Frequencies and percentages will be used to describe categorical variables.

The primary efficacy analysis will be based on the treated, response-evaluable . All patients who meet eligibility criteria, receive at least one dose of the study drug, and have evaluable 6-month outcomes will be included in the analysis of the primary and secondary endpoints, even if there are subsequent protocol deviations. Patients who withdraw from the study before on-treatment study effects can be assessed will be replaced

Analysis of Primary Endpoints

The 6-month PFS rate and its exact two-sided 95% confidence interval (CI) will be calculated. The primary analysis will be conducted after patients have been on treatment for 6 months. As secondary analysis, we will also evaluate the 6-month PFS as a time-to-event outcome using a non-parametric (Kaplan-Meier) or parametric Weibull model, based on the distribution of the survival function.

Analysis of Secondary Endpoints

The overall survival and progression free survival probabilities will be estimated using Kaplan-Meier method. The median survival and the corresponding 95% CI will also be provided.

**Columbia University Irving Medical Center
Herbert Irving Comprehensive Cancer Center
CUMC IRB – AAAT0174**

The estimates of the overall response rate (ORR), disease control rate (DCR), best overall response (BOR), duration of response, rate of in-field local control and out of field disease progression will be provided with the corresponding 95% CIs.

153 Size/Accrual Rate

The total sample of 18 patients is expected to be accrued over the course of two years (approximately 1 patient/month).

154 Stratification Factors

No stratification factors are applicable to this study.

155 Continuous Monitoring for Toxicity

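### ORR and DCR leave out treated patients who are never re-scanned instead of counting them as non-responders, so both rates may be overstated, and Section 15.2 gives a conflicting population

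*Combined protocol and SAP*

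**What the plan says.** Section 15.1 lists ORR and DCR as secondary endpoints and attaches the same restriction to each: "Only patients who have received at least one cycle of therapy and have had their disease re-evaluated will be considered evaluable for response". Section 13.2 has the matching definition, with baseline measurable disease added: "Only those patients who have measurable disease present at baseline, have received at least one cycle of therapy, and have had their disease re-evaluated". It makes one exception: "Patients who exhibit objective disease progression prior to the end of cycle 1 will also be considered evaluable".

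Section 15.2 describes the analysis set differently. Eligible patients who received at least one dose and "have evaluable 6-month outcomes will be included in the analysis of the primary and secondary endpoints". It adds: "Patients who withdraw from the study before on-treatment study effects can be assessed will be replaced". Section 6.5.3 has the same replacement rule. For reporting, Section 15.2 promises "The estimates of the overall response rate (ORR), disease control rate (DCR), best overall response (BOR), duration of response" and the in-field and out-of-field rates, each with a 95% CI. It plans no all-treated version of ORR or DCR and no sensitivity analysis.

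The protocol gives two dates for the first on-study scan. Section 13.1 says patients "should be re-evaluated for response every 6 weeks for 12 months beginning within -7d of Cycle 4, Day 1", which is about week 9, and the grid in Section 12 marks the first CT at the same visit. Section 5.2 and the calendar footnote on CT timing instead count every 6 weeks from Cycle 1 Day 1. Section 5.2 also mentions an assessment before radiation.

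**The concern.** Being re-evaluated is itself a post-treatment outcome. Patients who die or withdraw consent before any scan have not shown a response, yet under 15.1 and 13.2 they leave the analysis and do not count against the regimen. The exception in 13.2 covers progression documented objectively in cycle 1. It does not cover death without a scan, or departure without documented progression.

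ORR is named in the secondary objectives (Section 2), and these patients have a quoted median overall survival of 9.3 months (Section 3). With 18 patients, one or two early losses visibly move a percentage. The same patients are evaluable for toxicity from first treatment (Sections 13.2 and 15.6), so safety and response would be reported on different denominators.

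**Working it through.** **Plan's own design figures.** With p0 = 0.20, p1 = 0.45, n = 16 and success at 6 or more (Section 15.1), the exact binomial gives P(X ≥ 6 | 0.20) = 0.0817 and P(X ≥ 6 | 0.45) = 0.8024. Both meet the stated 0.10 and 80%. Inflating for dropout, 16/0.90 = 17.8, rounded up to 18. These figures reproduce and do not use ORR or DCR. No target is stated for either rate.

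**Direction and size.** Let N be the number treated, k the number never re-scanned and x the number of responders. A patient with no scan cannot be in x, so the numerator is the same either way:

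- planned rate = x/(N−k)
- all-treated rate = x/N
- ratio = N/(N−k), which is never below 1

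The same ratio applies to DCR, because stable disease also needs an assessment. For N = 18, with assumed numbers of responders:

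| k | Factor | x = 9 | x = 10 | x = 12 |
|---|---|---|---|---|
| 0 | 1 | 50.0% | 55.6% | 66.7% |
| 1 | 18/17 = 1.059 | 52.9% | 58.8% | 70.6% |
| 2 | 18/16 = 1.125 | 56.3% | 62.5% | 75.0% |
| 3 | 18/15 = 1.20 | 60.0% | 66.7% | 80.0% |

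The row k = 2 corresponds to the plan's dropout allowance (18 − 16 = 2), if those dropouts are never scanned.

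If withdrawn patients are replaced, N can exceed 18. For example, two unscanned patients replaced to restore 18 gives N = 20, k = 2 and a factor of 20/18 = 1.11.

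**What k might be.** The documents give no early death rate. As an assumption, take a constant hazard from the 9.3-month median, so the proportion dead by month t is 1 − 0.5^(t/9.3).

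- Week 6 (Section 5.2, calendar footnote): t = 42/30.44 = 1.38 months, giving 9.8%, or 1.8 of 18.
- Week 9 (Section 13.1, calendar grid): t = 63/30.44 = 2.07 months, giving 14.3%, or 2.6 of 18.

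These are upper figures for deaths without a scan if the early hazard is below average or some patients are scanned before death. If the pre-radiation assessment in 5.2 is a re-scan near Cycle 2 Day 1, and not the baseline scan, the week-3 figure is 5.0%, or 0.9 of 18. Consent withdrawals and missed scans would add to k.

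**Sections 15.1 and 15.2 side by side.** A patient who dies in week 5 without a scan is out under 15.1. Under 15.2 the same patient can be in, because death before 6 months is a known outcome under the Section 13.7 definition. Conversely, a patient who responds at the first scan and withdraws consent in month 4 is in under 15.1 but may have no evaluable 6-month outcome under 15.2. The text does not say which rule governs ORR and DCR.

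**The case against.** The strongest reply is that the protocol limits the losses. Sections 5.2 and 12 require patients who stop treatment for reasons other than progression, toxicity included, to continue scheduled scans, even on new therapy. Section 13.5.4 asks for every effort to document progression after symptomatic deterioration. Section 15.2 can be read as keeping early deaths. ORR and DCR are estimated without a test, the synopsis calls everything beyond the primary analysis exploratory, and the response-evaluable set is prespecified. The shift also lies inside the sampling error: the exact 95% CI for 10/18 is 30.8% to 78.5%.

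Much of this stands, and it rules out several stronger readings:

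- A reader might infer that all toxicity withdrawals are lost. Patients who complete a cycle and then stop should still be scanned.
- A reader might take 9 weeks as the exclusion window. It is the longer of two conflicting dates.
- A reader might conclude that the rates will be inflated against published response rates. Sections 3 and 4.2 quote 60-65% and 66% without denominators, so the documents cannot show this.

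The reply does not remove the gap. Death or consent withdrawal before any scan, departure during cycle 1 without documented progression, and missed scans are still dropped under 15.1 and 13.2. A wide interval does not help, because it is computed on the reduced set and does not reflect the selection. Section 15.2 contradicts 15.1 without overriding it.

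**Conclusion.** The point holds as a possible one-way overstatement of ORR and DCR. It occurs only if at least one treated patient is never re-scanned, so the rates may be overstated; the documents do not establish that they will be. For N = 18 the relative inflation is 6%, 12.5% or 20% for one, two or three such patients. A k of about 1 to 3 is plausible from deaths alone, but this rests on the constant-hazard assumption and on those deaths occurring unscanned.

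A reader might infer that the trial's conclusion is at risk. It is not: the rule of at least 6 of 16 uses 6-month PFS only. What is affected is the reading of two secondary efficacy rates, and the unreconciled populations in 15.1 and 15.2 leave their denominator open to choice after the data are seen.

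**What to change.** In Sections 13.2, 15.1 and 15.2, define one denominator for ORR and DCR: all eligible patients with baseline measurable disease who received at least one dose of study treatment, including any who are later replaced. Count patients with no post-baseline assessment as non-responders and as not having disease control. Report the re-evaluated set as a supportive analysis. State in 15.2 that the condition on 6-month outcomes does not apply to ORR and DCR, and that replacement does not remove a treated patient from these rates. Point the cross-references in 15.1, now to 13.5.2 and 13.5.3, to the definition in 13.2. The conflicting first-scan dates in 5.2, 12 and 13.1 should also be reconciled.

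The cost is a few sentences across three sections. No extra patients, visits or data are needed. Inclusion criterion 7 already requires measurable disease beyond the lesions planned for SBRT, so every eligible treated patient qualifies. The downside is that the reported rates become slightly less favourable.

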2 STUDY OBJECTIVES

21 Primary Objective

- To assess the efficacy of liver-directed SBRT when added to standard of care atezolizumab+chemotherapy as measured by the progression free survival rate at 6 months

22 Secondary Objective

- To assess the efficacy of adding liver-directed SBRT as measured by overall survival, progression-free survival, and the overall response rate
- To evaluate the feasibility and safety of adding liver-directed SBRT to standard of care atezolizumab+chemotherapy
- To describe the rate of in-field local control and out of field disease progression.

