The incidence of serious adverse events (SAEs) in the pooled population of patients receiving atezolizumab monotherapy was 41.2%. The most common SAEs were pneumonia (3.1%), dyspnea (2.8%), pyrexia (2.5%), UTI (1.9%) and pleural effusion, pulmonary embolism, and sepsis (1.3%).

Safety data is also available for atezolizumab in combination with chemotherapy, as proposed in this trial. In IMpower133 patients with ES-SCLC received atezolizumab 1200 mg IV on day 1, carboplatin at AUC 5 mg/ml/min on day 1 and etoposide 100 mg/m² IV on days 1-3 in 21 days cycles. In the combination atezolizumab+chemotherapy group, 94.9% of patients experienced a treatment related AE. 67.7% of patients experienced a grade 3-4 AE, compared to 63.3% with chemotherapy alone. The most common grade 3-4 AEs included neutropenia (22.7%), anemia (14.1%), and thrombocytopenia (10.1%) with combination therapy. Most immune related AEs (irAEs) were graded as 1-2, including rash (18.2%), hypothyroidism (12.6%), and hepatitis (6.1%) although grade 3-4 irAE also occurred including rash (2%), infusion-related reaction (2%), and hepatitis (1.5%). 3 patients in the atezolizumab+chemotherapy group experienced a death related to trial regimen including 1 from neutropenia, 1 from pneumonia, and one from an unspecified cause. 3 patients also died in the chemotherapy alone group (1 from pneumonia, 1 from septic shock, and 1 from cardiopulmonary failure).

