11.2 Treatment Regimen

Induction phase- four cycles of 21 days duration each will be administered as follows:

- Atezolizumab fixed dose of 1200 mg administered IV on day 1
- Carboplatin AUC=5 administered IV on day 1
- Etoposide 100 mg/m² on days 1, 2, and 3 of each cycle
- Stereotactic body radiation therapy administered to up to 3 liver lesions within +/-3 days of cycle 2 day 1.

Maintenance phase: atezolizumab 1200 mg administered on day 1 in 21 day cycles until withdrawal criteria are met as outlined in [**Section 5.5**](#).

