5. Survival visits are to occur every 4 to 6 months from the date of the 6 month Follow-up visit. Survival follow-up information will be collected via telephone calls, patient medical records, and/or clinic visits. Study staff may use a public information source (e.g., county records), when permissible, to obtain information about survival status only.
6. For atezolizumab, the initial dose will be delivered over 60 (± 15) minutes. If the first infusion is well tolerated, all subsequent infusions may be delivered over 30 (± 10) minutes until loss of clinical benefit.
7. For carboplatin and etoposide, drug should be administered as described in [Section 11](#)
8. Liver directed radiation with three doses of 10Gy delivered on alternate days up to three liver lesions measuring no greater than 5 cm each should be started within 7 (+/-3) days of C2D1
9. CT scans (with oral/IV contrast unless contraindicated) or MRI scans of the chest and abdomen.
10. A CT scan of the pelvis is required at screening and as clinically indicated or as per local standard-of-care at subsequent response evaluations.
11. Perform every 6 weeks (± 7 days) (approximately every two cycles) for 12 months following Cycle 1, Day 1 and then every 9 weeks (± 7 days) thereafter, regardless of treatment delays, until radiographic disease progression, withdrawal of consent, death, or study termination by the Sponsor, whichever occurs first. Patients who continue treatment beyond radiographic disease progression per RECIST v1.1 will continue to undergo tumor assessments every 6 weeks (± 7 days) or sooner if symptomatic deterioration occurs. For these patients, tumor assessments should continue every 6 weeks (± 7 days), regardless of time on study, until study treatment is discontinued.
12. If the patient discontinued study treatment for any reason other than disease progression (e.g., toxicity), tumor assessments will continue at the same frequency as would have been followed if the patient had remained on study treatment until radiographic disease progression, withdrawal of consent, death, or study termination by the principal investigator, whichever occurs first, even if the patient starts another anti-cancer therapy after study treatment discontinuation, unless consent is withdrawn.
13. Laboratory assessments to be done within 2 days prior to study drug infusion.

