Sequential boundaries will be used to monitor the toxicity rate throughout the trial. If an excessive number of dose-limiting toxicities are seen the DSMC will have the option of halting study accrual. The boundaries at which the study is halted are listed in Table 6. This is a Pocock-type boundary that yields at most a 5% probability of crossing the boundary when the rate of dose-limiting toxicity is equal to the acceptable rate 30%. The trial will be stopped if the number of dose limiting toxicities is equal to or exceeds b_n out of n patients with completed follow-up. This boundary is equivalent to testing the null hypothesis, after each patient, that the toxicity rate is equal to 0.3, using a one-sided level 0.023 test⁵⁴.

Table 6. Continuous monitoring of toxicity using Pocock-type boundary

Number of Patients, n	1	2	3	4	5	6	7	8	9	10	11	12	13	14	15	16	17	18
Boundary, b_n	-	-	-	4	5	5	6	6	7	7	7	8	8	9	9	10	10	10

156 Reporting and Exclusions

Evaluation of toxicity

All patients will be evaluable for toxicity from the time of their first treatment with the study drug.

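### The SBRT safety endpoint counts toxicity from the first drug dose with no analysis tied to irradiation, and feasibility has no endpoint

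*Combined protocol and SAP*

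**What the plan says.** Section 2.2 sets the secondary objective: "To evaluate the feasibility and safety of adding liver-directed SBRT to standard of care atezolizumab+chemotherapy". Section 15.1 turns the safety half into an endpoint, "The safety and tolerability of liver-directed SBRT will be determined by reported AEs, physical examinations and laboratory tests", and gives its analysis as "Frequencies of toxicities by grade according to NCI CTCAE (version 5.0) will be tabulated". No time window, irradiated denominator, attribution or confidence interval is given for it.

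Section 13.2 sets the start of evaluability: "All patients will be evaluable for toxicity from the time of their first treatment with atezolizumab, carboplatin and etoposide". Section 15.6 agrees: "All patients will be evaluable for toxicity from the time of their first treatment with the study drug". Radiation comes later. Section 11.2 has "Stereotactic body radiation therapy administered to up to 3 liver lesions within +/-3 days of cycle 2 day 1", and Section 5.2 uses the same margin. The study calendar footnote differs: SBRT "should be started within 7 (+/-3) days of C2D1".

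Two other sections deal with SBRT toxicity specifically. Section 10.3.1 requires causality to be judged separately for each protocol therapy, and its guidance names liver-directed radiation. Section 9.5 undertakes to assess SBRT-specific toxicity beyond that expected from the drugs, and lists toxicities of special interest in the radiation field.

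The endpoint list in Section 15.1 and the analyses in Section 15.2 contain no measure of whether SBRT was delivered. Section 15.2 also limits the secondary endpoints, of which safety is one, to patients with evaluable 6-month outcomes.

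**The concern.** SBRT is the only component added to standard treatment, so the safety question is what happens to patients once they are irradiated. The planned frequencies by grade start about three weeks too early for that question and include patients who never reach radiation. The background is also heavy. For the same drugs without SBRT, Section 4.1.4 reports that "67.7% of patients experienced a grade 3-4 AE, compared to 63.3% with chemotherapy alone". A whole-regimen frequency in 18 patients will be dominated by drug toxicity.

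Feasibility is a live question here. Radiation planning is done after cycle 1 (Section 5.2). Section 6.1 asks for a liver metastasis of 1 cm and states no upper size limit, whereas Section 8.2 restricts targeted lesions to 5 cm. Patients who withdraw early are replaced (Sections 6.5.3 and 15.2). As written, a patient who starts treatment but never receives SBRT could leave no trace in the efficacy or feasibility results.

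**Working it through.** **The plan's own safety figure.** The only numerical safety rule is the Table 6 boundary, stated to be crossed with probability at most 5% at a 30% dose-limiting toxicity rate. An exact binomial recursion over patients 1 to 18 gives 4.64%, and every entry satisfies the stated one-sided 0.023 test. The figure is correct. It is a monitoring rule and does not bear on how the safety endpoint is analysed.

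**Timing.** With 21-day cycles, cycle 2 day 1 falls 21 days after cycle 1 day 1.
- Section 11.2: 21 - 3 = 18 to 21 + 3 = 24 days after cycle 1 day 1.
- Calendar footnote, read as up to 7 + 3 = 10 days after cycle 2 day 1: as late as 21 + 10 = 31 days.

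On either reading, at least 18 days of drug toxicity precede the first fraction and count towards the endpoint.

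**Background.** Apply 67.7% (Section 4.1.4) to 18 patients and assume that SBRT adds nothing.
- Expected patients with a grade 3-4 event: 0.677 x 18 = 12.2.
- Exact (Clopper-Pearson) 95% interval for 12/18: 41% to 87%.
- P(15 or more of 18 | 0.677) = 0.12.

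Even a count of 15 would be unremarkable under the drugs alone, so an all-cause frequency by grade says little about SBRT.

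**Never-irradiated patients.** Suppose a toxicity that only SBRT can cause occurs in 20% of irradiated patients, and k of 18 are never irradiated. Both values are assumptions. The rate over all 18 is 0.20 x (18 - k)/18:
- k = 0: 20.0%
- k = 2: 0.20 x 16/18 = 17.8%
- k = 4: 0.20 x 14/18 = 15.6%

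The dilution is modest, but it always makes SBRT look safer.

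**Feasibility.** Exact 95% intervals for a completion proportion in 18 patients, with assumed counts:
- 16/18 = 88.9%: 65.3% to 98.6%
- 14/18 = 77.8%: 52.4% to 93.6%

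These are wide, but they are more than the plan now reports on feasibility.

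**Sections side by side.** Section 10.3.1 generates an SBRT attribution for each event, and Section 9.5 supplies a list of relevant toxicities. Section 15 uses neither. Section 9.5 gives no expected rate, window or irradiated denominator, and its explicit trigger is more than three replaced patients. It works as an enrolment-pause and dose-modification rule and does not define an analysis of the endpoint.

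**The case against.** The strongest reply is that SBRT safety is already addressed. Causality is assessed for each therapy, Section 9.5 commits to looking for excess SBRT toxicity, and Section 6.5.3 refers to comparison with previous studies. The objective concerns adding SBRT to a regimen, so reporting the toxicity of the whole regimen is legitimate. Section 15.1 does not forbid further breakdowns. All of this stands. A reader might infer that the safety objective goes unanswered. The documents do not support that, because the data are collected with attribution and the intent to examine SBRT toxicity is stated. What is missing is a defined analysis that uses them.

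A second reply is that a before/after split cannot isolate SBRT either, since chemotherapy continues through cycle 4 and atezolizumab beyond it. This also stands. The split removes events that cannot be due to SBRT; it does not show that later events are. Attribution alone is not enough, however. Section 9.6 accepts that attribution of hepatic and gastrointestinal toxicity may be unclear when the drugs are combined, and these overlap with the Section 9.5 list. The Section 10.3.1 scale also places unlikely relationships under its affirmative category. Onset date is an objective complement.

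A reader might also want to state what share of toxicity precedes SBRT. The documents give no distribution of onset times and the length of exposure will vary, so no such share can be supported.

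**Conclusion.** The point holds in a limited form. The endpoint named as SBRT safety has no analysis anchored to SBRT. It includes at least 18 days of pre-radiation toxicity and any never-irradiated patients, and it leaves the Section 9.5 and 10.3.1 information unused. Feasibility is named as an objective and has no endpoint. No stated number is wrong, and the all-treated table is not an error.

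The size can only be illustrated: 20% reading as 17.8% or 15.6% under the assumed non-delivery, against a background of about 12 of 18 with grade 3-4 events. The latter assumes that the rate from the cited trial carries over to this population. The safety half is the firmer part, because a better analysis is available at almost no cost. The missing feasibility endpoint alone would be little more than missing detail. The primary endpoint, sample size and Table 6 are unaffected.

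**What to change.** In Sections 15.1 and 15.2:

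1. Keep the all-treated toxicity table. State that safety uses all treated patients, not the Section 15.2 set with evaluable 6-month outcomes.
2. For patients who receive at least one SBRT fraction, add a table of adverse events by grade, with onset or worsening before versus on or after the first fraction. Include columns for SBRT-attributed events, stating which causality categories count, and for the Section 9.5 toxicities, with exact 95% confidence intervals. List never-irradiated patients separately.
3. State beside that table that the split excludes events that cannot be due to SBRT but does not establish causation, because the drugs continue.
4. Define feasibility as the proportion of eligible enrolled patients who start study treatment, including those later replaced, who receive all planned SBRT fractions within the protocol window. Report an exact 95% confidence interval and the reasons for non-delivery.
5. Before item 4 is final, reconcile the SBRT timing in Sections 5.2 and 11.2 with the calendar footnote.

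The cost is one additional table, one listing and one proportion. Event start dates and per-therapy causality are already required by Section 10.3.1. The documents do not show a case report form field for fraction dates; confirm that one exists, or add it. No more patients are needed.
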